10.2 Language of focus group discussions

Focus group discussions with health care workers will be in English. Focus group discussions with mothers, family members, religious leaders, community leaders, and traditional healers will be conducted in the local language. As shown in Table 3 above, these FGDs will be carried out in Chichewa in Lilongwe, and in Swahili in Dar es Salaam. In Odisha, there are two main local languages, Oriya and Hindi, so we will split the focus groups by language. For example, of the two FGDs with mothers of infants 0-3 months old, one will be conducted in Hindi and the other in Oriya. Similarly, in Karnataka, there are three local languages, Kannada, Marathi, and Hindi, and we will split FGDs by language.

10.3 In-depth interview eligibility criteria

Clinicians

Clinicians who are currently involved in providing support for IYCF will be eligible. They must either provide care directly to mothers or infants, provide advice to people who feed or support/influence feeding, or support or supervise other clinicians that directly provide care to mothers or infants. Clinicians who could be involved in the future in providing support for IYCF will also be eligible. Examples of doctors include OB/GYN, neonatologists, outpatient physicians, and pediatricians. The nurse cohort may include nurses, nurse midwives, and lactation nurses. We are also interested in speaking with community health workers that are connected to a study facility. While we provide clinician examples here, in-depth interviews may not be limited to these types of providers.

We will exclude clinicians who have been at the facility for less than six months.

Of note, some sites might determine that the nurse cohort or other health care worker cadres are better suited as a focus group discussion instead of an in-depth interview. In this case, the eligibility criteria remain the same, and interview facilitators will use the same interview guide with clearly marked questions for the focus group discussions.

Ministry of Health and other government officials

Any members of the MOH or other government officials whose responsibilities include supporting (e.g., human resource or budget) or participating in IYCF studies, quality improvement initiatives, or implementation programs, or whose support would be necessary for the success of an IYCF program, are eligible for inclusion.

We will exclude officials who have been in their post for less than six months.

Supply chain experts

Individuals who are involved in or provide oversight for the local supply chain of resources potentially needed for an IYCF intervention, or who has expert knowledge about local supply chains, is eligible for inclusion. These may be government employees or staff of independent NGOs, either domestic or international.

The interviews will include people knowledgeable about centralized, systemic distribution of supplies needed for an IYCF intervention, such as managers of drug stores, vaccine depots, or public health supplies. We will also include individuals in the local study facility that order or receive the supplies needed for an IYCF intervention.

Human milk bank experts

Anyone who has knowledge or experience with local human milk banks or the establishment and operation of human milk banks in other LMICs is eligible for inclusion. This could include those who have established HMB, have tried to, or are currently planning their development. This could include global leaders or those in-country that have experience with HMB or are familiar with the concept. Examples of in-country individuals could be community leaders involved with nutrition or newborn or maternal health.

Mothers (6-month extension)

Mothers chosen and consented for IDIs will include those currently enrolled in the prospective cohort. Additionally, their infants need to be between 9 and 12 months of age. These mother-infant pairs will be divided by growth status (faltering vs not faltering based on z-scores) and by sex of the infant.

10.4 Recruitment

The recruitment method for each population will be somewhat different, as described below:

Clinicians and health care workers

Site clinicians and health care workers will be approached in person by study staff members when convenient. Identification of clinicians might come from site leadership members or other clinicians that participate in the focus group discussions.

Mothers of LBW infants

Recruitment of mothers of LBW infants for the focus group discussions will be done by study staff members during clinic hours. They will approach women at a convenient time when they are at the facility. This could be before discharge or when the woman comes in for a postnatal visit for either herself or her baby.

Family members of mothers of LBW infants

Recruitment of family members of mothers of LBW infants will be done by study staff members. Individuals can be recruited in two primary ways: 1) through the mothers that participate in the FGDs or 2) if they accompany the woman to a postnatal visit at the facility. A secondary method of recruitment is through the facility's Community Advisory Board that provides outreach to community members.

Religious and community leaders

Religious and community leaders will be recruited by either study staff members or Community Advisory Board members.

Traditional healers

Traditional healers will be recruited by study staff members or Community Advisory Board members.

MOH and other government officials

Recruitment of Ministry of Health or other government officials will be done by senior study staff members and project partners. We will recruit by the individual's function in the government, and their relation to IYCF policies. Recruitment might also be done by snowball sampling as interviewees might identify others with expert knowledge in IYCF practices, policies, and guidelines.

Supply chain experts

Recruitment of supply chain experts will be done by study staff members. We will request contact information for individuals that are involved with the distribution of IYCF supplies as well as facility staff members that order and receive IYCF supplies. We will employ snowball sampling for the identification and recruitment of supply chain experts.

Human milk bank experts

In India only, human milk bank experts will be recruited by study staff members. We will request contact information for individuals to conduct interviews with and employ snowball sampling for further recruitment.

Mothers (6-month extension)

Mothers will be recruited by study staff in person when they are at facility for a clinic visit or via phone. They will approach women at a convenient time when they are at the facility. All mothers who will be approached will be current participants in the prospective cohort study. Study staff members will approach these individuals and read the consent form and recruitment script in private. If recruited for the IDIs, the study staff will schedule a time to conduct the interview either at home or before/after a scheduled facility visit.

10.5 Informed consent

The study team will obtain written informed consent from all participants before the start of the interview or focus group discussion.

10.6 Conduct of groups and interviews

If key informants are unable to participate in FGDs then they will be interviewed individually or in pairs.

All parties participating in a focus group discussion or interview will be provided a study fact / recruitment sheet prior to the interview or focus group.

All IDIs and FGDs will be conducted by a facilitator and 1-2 note takers in a private location that is convenient for participants. If possible, the interviews may be done at the facility or participant's office, as appropriate. At the study start, trainers may also attend to observe the facilitator to ensure the quality of data collection. All discussions will be audio recorded. Notes for FGDs and IDIs will be taken in either English or the local language based on the note taker, and any notes taken in the local language will be translated into English immediately following the conversations. Discussions will be analyzed using rapid qualitative analysis, which involves taking notes during interviews and focus groups then writing summaries of key messages immediately following the conversation based on recall of the conversation and the notes.

For the extension: The interview guides will be analyzed using thematic coding of the interview transcripts

10.7 Data analysis

Messages will be organized by themes/topics in the knowledge management tool. Content of each transcript or theme/topic will be reviewed on a regular basis (after every several interviews/focus groups). Learnings from earlier conversations can inform iterations of interview and focus group guides to explore some areas more in-depth or new areas of interest. A comprehensive analysis of the key messages will be done at the end of the data collection phase to inform intervention, study, and implementation recommendations.

Audio recordings of IDIs and FGDs may be transcribed and translated for potential future analyses and to ensure that a complete data set is available. All IDIs performed during the extension will be transcribed and translated.

10.8 Schedule of data collection

Each site is planning for a total of 8-12 focus groups. The focus groups will be broken down by respondent type, with 2-4 focus groups (consisting of approximately 5-8 participants per group) with each of the following cohorts: mothers, family members, and recognized community members (includes community leaders, traditional healers, and religious leaders). We expect a maximum of 384 individuals participating in focus groups across all sites.

Each site is planning for 6-12 semi-structured in-depth interviews with non-clinicians. The interviews will be broken down by respondent type, with 2-4 interviews among each of the following cohorts: government officials, supply chain experts, and human milk bank experts. Sites will also conduct in-depth interviews with clinicians with a maximum of 40 clinicians and or community health workers at each study facility. For example, this could be up to 24 clinician interviews in Malawi's two study facilities. Sites will determine the number of clinicians and clinician roles included in the interviews based on who would be most appropriate to speak with in their context and the number of clinicians on staff. Dependent on the number and size of facilities, as well as individual staffing characteristics, there will be up to 38-84 data collection events per site over the period allotted in the study timeline. The timing of data collection will depend on the subjects' and interviewers' availability, and sites and the study team will be flexible with the proposed timing. We expect a maximum of 288 individuals participating in in-depth interviews across all sites. For the 6-month extension, in total, up to 20 mothers per study site will participate in the IDIs. We expect a maximum of 80 mothers participating in the in-depth interviews across all sites.

10.9 Ethics

The risks to participants in the FGDs are the possibility of feeling uncomfortable sharing their opinions or hearing the opinions of others, or having others from the group think poorly of them because of their opinions or the experiences they choose to share. However, participants will be told that they do not need to answer any questions that they are not comfortable answering, and participants can choose what they do and do not want to share with the group. All participants will be asked to keep the discussion confidential and not share the identities of participants, but we will not be able to ensure compliance with this request. Again, participation, lack thereof, or withdrawal of consent will not affect clinical care of patient participants, or employment of clinical staff participants.

The risk to participants in the IDIs is the possibility of feeling uncomfortable sharing their opinions. However, participants will be told that they do not need to answer any questions that they are not comfortable answering and participants can choose what they do and do not want to share.

Participants in IDIs and FGDs will receive reimbursement for their participation, as identified by sites (Table 9)

Table 9: Reimbursements for participation in FGDs and IDIs

Study Site	Incentive
Karnataka	Participants will receive loss of wages, travel allowance and dearness allowance (DA) for each study visit, not to exceed US \$15
Odisha	Participants will receive loss of wages, travel allowance and dearness allowance (DA) for each study visit, not to exceed US \$15
Lilongwe	Participants will receive the Malawi Kwacha equivalent to US \$10 for participating. This amount is to cover the costs of transport expenses to and from the interview / focus group. Snacks and sodas will also be provided for focus group participants.
Dar es Salaam	Participants will receive travel allowances for participating in the focus group, not to exceed US \$25.

Participants in IDIs and FGDs will not receive direct benefits from participating, other than transportation reimbursement in some sites. They may feel personal satisfaction knowing that they are contributing to the development of an IYCF that may benefit themselves or others in their community.

11 Desk research

11.1 Chart review

The goal of the chart review is to document the routine and SOC at each site prior to the start of the study. Although LIFE is non-interventional, the extra attention that the study will bring to infant feeding issues in the facilities may affect the SOC we observe. In particular, having an observer present may alter clinicians' or mothers' behaviors in ways that are difficult to measure. The chart review data will allow us to compare the SOC we observe in LIFE to what was occurring just before LIFE began. This will augment our picture of the true SOC.

We will review 155 retrospective charts of LBW births at each study site; the number of individuals included will be up to 155 mothers (to account for errors) and their infants (up to 200 infants, accounting for twins). Cases will be selected by the inclusion/exclusion criteria (see below), taking all qualifying cases that occurred as chronologically close as possible to the start of the LIFE study. Since the purpose is to understand routine and SOC before the LIFE study, we will not review any cases admitted after the study launch.

We will abstract information on infant feeding volume and frequency, status at discharge and information given, as well as any available health outcomes (anthropometrics, morbidities, etc.). As much as possible, the data collected in the chart review will mirror that collected in the in-facility observations.

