8.5 Informed consent

Women will provide written informed consent to participate in the in-facility observations. Each participant will consent to:

- observations of the care she receives from clinical staff,
- observations of the feeding behaviors of her and her infant,
- verbal interviews with study staff roughly every three hours until discharge, and
- access to her medical chart and her baby's medical chart by study staff including HIV status, if available.

In the case of illiteracy, we will use a thumbprint for the woman's signature, with an additional signature from an impartial witness to the consent process.

In the case that a mother consents to participate but asks a surrogate to answer questions for her, the action required will be country-specific in alignment with site requirements:

- Tanzania: Mother will complete and sign an additional "caretaker consent form", authorizing a surrogate to share information about her.

- India: Mother's signed consent is sufficient; no further action required.
- Malawi: Only allowed in the case that the mother is in the ICU and unable to answer: the trusted guardian will sign a separate consent form (same version as mother's consent form)

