8.6.1 During daytime shifts

As shown in Table 4, the observation schedule will involve continuous observation in the first three hours, plus regular “spot checks” until discharge. If the facility has a regular feeding schedule for infants, then the spot checks will coincide with that schedule, in order to observe as many feeds as possible. If the facility does not have a regular feeding schedule, then facility staff will alert the observer when a feed is taking place. If the facility staff are not present at the time, then a mother or family member may also alert staff that a feed is taking place. If not notified of a feed within 3-4 hours of the previous spot check, the observer will perform an unprompted spot check. In this way, the spot checks will be mainly prompted by feeding behavior, but will take place at a minimum every 3-4 hours, when the observer will ask about any feeding behavior since the previous spot check.

Observers will use structured checklists to record information on all infant feeds. Since the first hours of the child's life will not have been observed, the observer will ask the mother and clinicians about the timing and nature of any feeds that happened prior to observation. If any feeding behavior takes place during the spot checks, the observer will observe and record it.

If the infant enters the NICU or other sick baby unit (SBU), the observer will follow the infant to the NICU/SBU. If the mother and infant are separated, the observer will follow the infant. When the mother is interviewed before discharge, the observer will ask about her nutrition and lactation during the period of separation from the infant.

In the intervals between spot checks, the observer will collect information on WASH for feed preparation in the facility (up to 5 observations), using structured observations of clinicians performing feeding vessel preparation and storage.

Table 4: Observation schedule

Directly after written consent is given:

1.	Before initiating the baseline interview with the mother, conduct the maternal chart check, (include HIV status) and baby chart check
2.	Interview the mother about her demographics, delivery experience, and feeding behavior since the infant's birth. Take baseline anthropometric measurements for the baby.

3.	Observe the mother/infant pair for the first three hours continuously, noting all feeds and feeding behavior of infant and mother.

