8.7 Sample size

Each site will carry out 35 to 45 observations, with a minimum of three at each facility but with no greater than 45 mothers. This accounts for participants lost to follow up. This equates to 35 mothers and up to 60 infants to account for twins; thus, a total of up to 95 individuals per site. Although the total number of mothers and infants above add up to 105, we will never exceed 95 individuals given the twinning rates in the sites. The goal of this sample is to get a deep understanding of the kinds of feeding experiences that LBW infants might have in each site. The sample size was determined by timeline and budget constraints; sites felt that this number of intensive in-facility observations was achievable.

This sample may not be representative of all LBW infants at a site. However, the rich descriptive results from these cases will give an informative picture of the range of experiences at each site.

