Bill and Melinda Gates Foundation	Funder & Steering Committee Member
Harvard TH Chan School of Public Health/ Ariadne Labs	Project Leadership. Ariadne Labs will provide both scientific and management leadership for the project design, monitoring and implementation of this project, overseeing all partners and ensuring their coordination.

Ariadne Labs is a joint center between Brigham and Women's Hospital and the Harvard T.H. Chan School of Public Health. Ariadne Labs' mission is to create scalable health care solutions that deliver better care at the most critical moments in people's lives, everywhere. Ariadne Labs' solutions and tools are simple, practical and designed to have global impact. The work of Ariadne Labs is rooted in rigorous scientific methodology and best practices in industry for implementation. Each body of work is built on a foundation of innovative use of informatics, measurement, implementation and improvement science, and professional program management.

Ariadne Labs has unique experience and success in designing and managing successful large scale, complex trials in maternal and newborn health. Areas of expertise include: large scale coordination; complex trial implementation in Asia and Africa; applied solutions and driving scale; data capture and feedback; community and facility-based follow up; formative and qualitative research; and practical field applications of solutions.

Jawaharlal Nehru Medical College (JNMC), Belgaum Site Implementation. The central team of investigators from the Women's and Children's Health Research Unit (WCRU) of JNMC Belgaum will lead the implementation of the project in 2 geographies/sites in India (5 facilities in Karnataka State and 3 facilities in Odisha State).

The facilities in Karnataka with capacity to eventually run an efficacy trial are located in different parts of the state. Clinical and cultural practices are known to be significantly different between the facility sites, as such it is recommended to capture data from the 5 sites. Some of the data collection support processes have been centralized to do this in an efficient way.

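### The check on whether LIFE changed care sets pre-launch charts against mainly observed feeding, so under-recording in charts could pass for a change in care

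*Combined protocol and SAP*

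**What the plan says.** Section 11.1 (Chart review) gives the reason for the comparison: "having an observer present may alter clinicians' or mothers' behaviors in ways that are difficult to measure". Its answer is this: "The chart review data will allow us to compare the SOC we observe in LIFE to what was occurring just before LIFE began". The pre-launch source is fixed: "We will review 155 retrospective charts of LBW births at each study site". The section bars review of any case admitted after launch. The items abstracted include feeding volume and frequency, discharge status and available health outcomes. On alignment it says: "As much as possible, the data collected in the chart review will mirror that collected in the in-facility observations".

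During LIFE the method differs. Section 8.6.1 says: "Observers will use structured checklists to record information on all infant feeds". It sets three hours of continuous observation, then spot checks at least every 3 to 4 hours, at which the observer asks about feeds since the last check. Section 8.6.2 says that no observers work overnight and that charts are used each morning to fill the gap. Each site observes 35 to 45 pairs (Section 8.7).

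Section 8.5 already obtains consent to the mother's chart and to her baby's "medical chart by study staff including HIV status, if available". Section 8.8 plans descriptive statistics and a comparison with guidelines. Section 11.1 gives no analysis method for the before/during comparison.

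**The concern.** A before/during comparison isolates change in care only if both periods are measured the same way. Here one period is known from what clinicians wrote down. The other is known mainly from a trained observer with a checklist who also questions mothers or clinicians. Collecting the same items does not make the recording equally complete.

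If charts omit feeds, care that stayed the same will look more frequent or better supported under LIFE. A real fall could equally be hidden. This is the plan's only before/during check on whether the study's presence altered care. A source artefact could be read as an effect of the observers, or could falsely reassure that there was none.

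**Working it through.** **Plan's own figure.** The protocol attaches no effect size or precision to this comparison, and Section 8.7 says that the observation number came from timeline and budget. The one precision figure given elsewhere (Section 9.12: n = 250, 5%, ±2.7%) reproduces: 1.96 × √(0.05 × 0.95 / 250) = 2.7 points. The same formula is used for precision below.

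**Inputs from the protocol:** 155 charts and 35 to 45 observed pairs per site; observers by day; charts for the night.

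**Assumed, because the protocol does not say:** 8 evenly spaced feeds per 24 hours in both periods; a share s = 0.5 to 0.9 of feeds charted; 8 to 12 unobserved hours, so f = 1/3 to 1/2 of feeds fall at night; daytime capture complete; night feeds taken from charts only.

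**Spurious rise in feed frequency with no change in care**

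- Before: 8s.
- During: 8[(1 − f) + f·s].
- Apparent rise: (1 − f)(1 − s)/s.

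| Night hours | s | Before | During | Apparent rise |
|---|---|---|---|---|
| 12 | 0.9 | 7.2 | 4 + 3.6 = 7.6 | 6% |
| 8 | 0.9 | 7.2 | 5.33 + 2.40 = 7.73 | 7% |
| 12 | 0.5 | 4.0 | 4 + 2 = 6.0 | 50% |
| 8 | 0.5 | 4.0 | 5.33 + 1.33 = 6.67 | 67% |

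If mothers recalled every overnight feed at the morning check, the during figure would be 8. The rise would then be 8/7.2 − 1 = 11% to 8/4 − 1 = 100%. That is the ceiling.

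**Masking.** The two records agree despite a true fall of 1 − s/[(1 − f) + f·s]. At s = 0.9 this is 1 − 0.9/0.95 = 5% (12 hours) and 1 − 0.9/0.967 = 7% (8 hours). At s = 0.5 it is 1 − 0.5/0.75 = 33% and 1 − 0.5/0.833 = 40%.

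**Visibility against sampling error.** Take a yes/no feeding practice with true prevalence p in both periods, charted with probability s and always seen by observers. The last condition makes this an upper bound. The spurious gap is p(1 − s). The last column is the chance that a 95% interval for the difference excludes zero, with 155 charts against 35 or 45 observed and clustering ignored.

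| p | s | Gap (points) | Interval excludes zero |
|---|---|---|---|
| 30% | 90% | 3 | 6% to 7% |
| 50% | 80% | 10 | 19% to 22% |
| 80% | 70% | 24 | 86% to 92% |

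Mild under-recording is lost in noise. Heavier under-recording looks like a study effect.

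**After the fix.** With charts on both sides and equal completeness, the spurious difference is 8s − 8s = 0 for any s. If completeness moves from s₀ to s₁ under LIFE, the residual bias is s₁/s₀ − 1. For example, a move from 0.70 to 0.80 (assumed) gives 14%. Precision for a practice at 50% in both periods is 1.96 × √(0.25/155 + 0.25/n) = 18.3 points at n = 35 and 16.6 points at n = 45.

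**The case against.** The strongest reply is that little depends on this comparison. Section 11.1 gives the chart review's goal as documenting care before the study and says that it augments the picture of standard of care. No decision rule uses the result, and Section 8.7 concedes that the observed sample may not be representative. That stands. It limits the importance of the point but does not make the comparison interpretable.

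A second reply is that mitigation exists: the chart checks at consent (Table 4), the morning chart checks (Section 8.6.2) and the back-end comparison of data sources (Section 13.1). None of these is a full feeding abstraction on the chart-review form, and the back-end check is generic.

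Two stronger readings are tempting and are not supported.

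- A reader might take the LIFE record as complete and quote 11% to 100% as the expected distortion. Overnight data come from charts, and Section 8.6 accepts that continuous recording is not possible. Under-recording is itself an assumption. Discharge status and anthropometry, which are also abstracted, need not share the bias.
- A reader might infer a facility-mix mismatch. Observations are planned only "with a minimum of three at each facility", while Section 14, Table 10 says of Karnataka: "Clinical and cultural practices are known to be significantly different between the facility sites". But Section 11.1 does not state how the charts are split across facilities, and a floor of three is not an allocation. No mismatch is shown.

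**Conclusion.** The concern holds for feeding items. The planned comparison changes period and data source together, and nothing in the protocol separates them. Its size is unknown because chart completeness is not given. Under the stated assumptions the artefact is about 6% to 7% in feed frequency at 90% completeness and 50% to 67% at 50%. These figures take daytime observation as complete, so missed daytime feeds would lower them. The documents do not show that charts in fact under-record, or that the study's description of standard of care rests on this comparison. It is a supporting check worth correcting because the correction is cheap.

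**What to change.** Amend Section 11.1 as follows.

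1. Add an explicit exception to the bar on post-launch cases. Apply the chart-review form to the birth-stay charts of the 35 to 45 observed pairs per site, with the abstractor blind to the observer record.
2. Make the before/during comparison of feeding items chart to chart, restricted to births that meet both sets of eligibility criteria. Section 11.1.1 says that night births are in the chart review but not in the observations, and it drops facility deaths within 72 hours.
3. In the observed pairs, report agreement between the observer record and the same infant's chart for daytime feeds only, as an estimate of chart completeness. Overnight entries come from the chart and would agree by construction.
4. State that the chart-to-chart comparison assumes charting completeness does not itself change under LIFE. Item 3 measures completeness during LIFE only and cannot test this.

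Tabulating the comparison by facility is optional.

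**Cost.** There are 35 to 45 extra abstractions per site, or 140 to 180 over four sites, against 4 × 155 = 620 already planned. Chart access is already in the Section 8.5 consent, and the form is needed anyway. The during-LIFE chart sample is small, and the eligibility restriction makes it smaller, so the interval will be no narrower than the 17 to 18 points shown for a 50% practice.
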